9.1.1 Tumor response evaluation

To assess objective response or future progression, it is necessary to estimate the overall tumor burden at baseline and use this as a comparator for subsequent measurements. Measurable disease is defined by the presence of at least one measurable lesion.

When more than one measurable lesion is present at baseline, all lesions up to a maximum of 3 lesions total in the targeted liver lobe and 3 lesions in the non-target liver lobe and additionally 3 lesions outside of liver will be evaluated. We will use m-RECIST for the evaluation of liver lesions which is based on the size of enhancing portion of the lesions and not the entire size of the lesion. This has shown to be much more accurate in evaluation of HCC compared to RECIST and RECIST 1.1 [42].

Target lesions should be selected on the basis of their size (lesions with the longest diameter), be representative of all involved organs, but in addition should be those that lend themselves to reproducible repeated measurements. It may be the case that, on occasion, the largest lesion does not lend itself to reproducible measurement in which circumstance the next largest lesion which can be measured reproducibly should be selected. Pathological nodes which are defined as measurable and may be identified as target lesions must meet the criterion of a short axis of ≥ 15 mm by CT scan. Only the short axis of these nodes will contribute to the baseline sum. All other pathological nodes (those with short axis ≥ 10 mm but < 15 mm) should be considered non-target lesions. Nodes that have a short axis < 10 mm are considered non-pathological and should not be recorded or followed. If lymph nodes are to be included in the sum, then as noted above, only the short axis is added into the sum. The baseline sum diameters will be used as reference to further

characterize any objective tumor regression in the measurable dimension of the disease. All other lesions (or sites of disease) including pathological lymph nodes should be identified as non-target lesions and should also be recorded at baseline. Measurements are not required and these lesions should be followed as ‘present’, ‘absent’, or in rare cases ‘unequivocal progression’. For assessment of abscopal response, any of the target lesions identified at baseline will be measured and followed for abscopal response. This target lesion should not be a target of injection or biopsy. The abscopal response is defined as a shrinkage of $\geq 20\%$ from baseline in any target non-manipulated metastatic lesion identified at baseline.

Evaluation of Target Lesions

Complete Response (CR): No intramural arterial enhancement in all target lesions.

Partial Response (PR): At least a 30% decrease in the sum of the diameters of viable (enhancement in the arterial phase) target lesions.

Progressive Disease (PD): At least a 20% increase in the sum of the diameters of viable target lesions.

Stable Disease (SD): Features classifiable as neither partial response nor progressive disease.

Evaluation of Non-Target Lesions

Complete Response (CR): No intramural arterial enhancement in all target lesions.

Partial Response (PR): At least a 30% decrease in the sum of the diameters of viable (enhancement in the arterial phase) target lesions.

Progressive Disease (PD): At least a 20% increase in the sum of the diameters of viable target lesions.

Stable Disease (SD): Features classifiable as neither partial response nor progressive disease.

Although a clear progression of “non-target” lesions only is exceptional, the opinion of the treating physician should prevail in such circumstances, and the progression status should be confirmed at a later time by the review panel (or Principal Investigator).

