Note: Cystic lesions that meet the criteria for radiographically defined simple cysts should not be considered as malignant lesions (neither measurable nor non-measurable) since they are, by definition, simple cysts.

‘Cystic lesions’ thought to represent cystic metastases can be considered as measurable lesions, if they meet the definition of measurability described above. However, if non-cystic lesions are present in the same patient, these are preferred for selection as target lesions.

Target lesions. All measurable lesions up to a maximum of 5 lesions per treated liver lobe will be identified as target lesions and recorded and measured at baseline. Target lesions should be selected on the basis of the size of their enhancing portion but in addition should be those that lend themselves to reproducible repeated measurements. It may be the case that, on occasion, the largest lesion does not lend itself to reproducible measurement in which circumstance the next largest lesion which can be measured reproducibly should be selected.

Non-target lesions. All other lesions (or sites of disease) including any measurable lesions over and above the 5 target lesions should be identified as **non-target lesions** and should also be recorded at baseline. Measurements of these lesions are not required, but the presence, absence, or in rare cases unequivocal progression of each should be noted throughout follow-up.

Methods for Evaluation of Measurable Disease

All measurements should be taken and recorded in metric notation using a ruler or calipers. All baseline evaluations should be performed as closely as possible to the beginning of treatment and never more than 4 weeks before the beginning of the treatment.

The same method of assessment and the same technique should be used to characterize each identified and reported lesion at baseline and during follow-up.

Multiphase Liver Mass Protocol CT and MRI: Liver mass protocol MRI is the preferred imaging modality in this study. This guideline has defined measurability of lesions on CT scan based on the assumption that CT slice thickness is 5 mm or less. If CT scans have slice thickness greater than 5 mm, the minimum size for a measurable lesion should be twice the slice thickness.

FDG PET/CT: PET/CT is not an ideal modality for evaluation HCC at baseline or after therapy.

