Ultrasound: Ultrasound is not useful in assessment of lesion size and should not be used as a method of measurement. Ultrasound examinations cannot be reproduced in their entirety for independent review at a later date and, because they are operator dependent, it cannot be guaranteed that the same technique and measurements will be taken from one assessment to the next. If new lesions are identified by ultrasound in the course of the study, confirmation by CT or MRI is advised. If there is concern about radiation exposure at CT, MRI may be used instead of CT in selected instances.

Tumor markers: Tumor markers alone cannot be used to assess response. If markers are initially above the upper normal limit, they must normalize for a patient to be considered in complete clinical response.

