9.1.2 Evaluation of Best Overall Response

The best overall response is the best response recorded from the start of the treatment until disease progression/recurrence (taking as reference for progressive disease the smallest measurements recorded since the treatment started). The patient's best

response assignment will depend on the achievement of both measurement and confirmation criteria.

For Patients with Measurable Disease (*i.e.*, Target Disease)

Target Lesions	Non-Target Lesions	New Lesions	Overall Response	Best Overall Response when Confirmation is Required*	
CR	CR	No	CR	≥4 wks. Confirmation**	
CR	Non-CR/Non-PD	No	PR	≥4 wks. Confirmation**	
CR	Not evaluated	No	PR		
PR	Non-CR/Non-PD/not evaluated	No	PR	Documented at least once ≥4 wks. from baseline**	
SD	Non-CR/Non-PD/not evaluated	No	SD		
PD	Any	Yes or No	PD	no prior SD, PR or CR	
Any	PD***	Yes or No	PD		
Any	Any	Yes	PD		

* See RECIST 1.1 manuscript for further details on what is evidence of a new lesion.
 
** Only for non-randomized trials with response as primary endpoint.
 
*** In exceptional circumstances, unequivocal progression in non-target lesions may be accepted as disease progression.
					

Note: Patients with a global deterioration of health status requiring discontinuation of treatment without objective evidence of disease progression at that time should be reported as “symptomatic deterioration.” Every effort should be made to document the objective progression even after discontinuation of treatment.
					

For Patients with Non-Measurable Disease (*i.e.*, Non-Target Disease)

Non-Target Lesions	New Lesions	Overall Response
CR	No	CR
Non-CR/non-PD	No	Non-CR/non-PD*
Not all evaluated	No	not evaluated
Unequivocal PD	Yes or No	PD
Any	Yes	PD

* ‘Non-CR/non-PD’ is preferred over ‘stable disease’ for non-target disease since SD is increasingly used as an endpoint for assessment of efficacy in some trials so to assign this category when no lesions can be measured is not advised
		

Duration of Response

Duration of overall response: The duration of overall response is measured from the time measurement criteria are met for CR or PR (whichever is first recorded) until the first date that recurrent or progressive disease is objectively documented (taking as reference for progressive disease the smallest measurements recorded since the treatment started).

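### The non-target lesion criteria in Section 9.1.1 repeat the target-lesion criteria, so the 9.1.2 response table lacks its non-target input, and complete response carries an unscheduled tumor-marker condition

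*Combined protocol and SAP*

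**What the plan says.** All references are to the combined protocol and SAP.

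- **Section 9.1.1, target block and non-target block.** Both blocks give the same text. CR is "No intramural arterial enhancement in all target lesions". PR is "At least a 30% decrease in the sum of the diameters of viable (enhancement in the arterial phase) target lesions". PD is "At least a 20% increase in the sum of the diameters of viable target lesions". SD is whatever is neither PR nor PD.
- **Sections 9.1 and 9.1.1, follow-up of non-target lesions.** Section 9.1 says: "Measurements of these lesions are not required, but the presence, absence, or in rare cases unequivocal progression of each should be noted throughout follow-up". Section 9.1.1 repeats it: "Measurements are not required and these lesions should be followed as" present, absent or, rarely, unequivocally progressing.
- **Section 9.1.1, closing sentence of the non-target block.** Where only non-target lesions progress, the treating physician's view takes precedence, subject to later confirmation by the review panel or Principal Investigator.
- **Section 9.1.2, overall-response table.** It combines target status with a separate non-target status of CR, Non-CR/Non-PD, PD or not evaluated. A footnote adds: "In exceptional circumstances, unequivocal progression in non-target lesions may be accepted as disease progression".
- **Section 9.1, tumor markers.** Markers alone cannot be used to assess response, but: "If markers are initially above the upper normal limit, they must normalize for a patient to be considered in complete clinical response".
- **Section 10.5.3.** The CR rate is to be reported with an exact 95% confidence interval. Patients with no response assessment for reasons other than early progression or death are left out of the denominator.

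**The concern.** The table in 9.1.2 works only if someone can assign a non-target status that does not simply restate the target status. The block in 9.1.1 that should define it describes the target lesions a second time. A reader scoring strictly from 9.1.1 would call non-target CR whenever the targets have lost enhancement, whatever has happened elsewhere. Another reader, working from the follow-up terms and the table, would reach a different overall response for the same patient. What is at stake is mainly the CR rate, a planned efficacy summary.

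The marker sentence raises a smaller question of the same kind. It attaches a condition to complete response that the definitions in 9.1.1 and 9.1.2 do not contain. Applied as written, it would affect only patients who happen to have a marker result from routine care.

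**Working it through.** The plan gives no figure to reproduce here, so the check is a comparison of the sections.

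**1. The two blocks in 9.1.1.** Four of four definitions are identical. The CR, PR and PD lines in the non-target block name target lesions. SD is the remainder after PR and PD, so it depends on target lesions too.

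**2. Would changing one word repair it?** No. PR and PD need a sum of diameters, and 9.1 and 9.1.1 say non-target lesions need not be measured. The 30% and 20% rules cannot be applied to them even with the noun corrected.

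**3. Does 9.1.1 supply what 9.1.2 needs?** The table needs CR, Non-CR/Non-PD or PD. Section 9.1.1 does not define Non-CR/Non-PD, and it defines the other two by the wrong lesions. It also offers non-target PR and SD, for which the table has no entry.

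**4. Effect on overall response, no new lesions.** By the table, overall response is PD if either status is PD. It is CR if both are CR. It is PR if the target is CR and the non-target is Non-CR/Non-PD or not evaluated. Otherwise it is the target status. Under the literal wording the non-target status follows the target status (copied PR and SD are taken as Non-CR/Non-PD), so overall response equals target response. The two readings differ in five combinations:

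| Target | Non-target, assessed in its own right | Literal 9.1.1 | 9.1.2 table |
|---|---|---|---|
| CR | Non-CR/Non-PD | CR | PR |
| CR | not evaluated | CR | PR |
| CR | PD | CR | PD |
| PR | PD | PR | PD |
| SD | PD | SD | PD |

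In all five the literal reading gives the better result. The last three have another route to PD, through the 9.1.2 row and footnote and the physician sentence in 9.1.1. The first two have no such sentence to rescue them: the table row exists, but the copied CR definition prevents a reader from reaching it.

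**5. Size.** One patient moved from PR to CR changes the CR rate by 1/(number evaluable):
- 30 evaluable: 1/30 = 3.3 points.
- 25 evaluable (assumed): 1/25 = 4.0 points.
- 20 evaluable (assumed): 1/20 = 5.0 points.

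The documents do not say how many patients would have target CR with a persisting non-target site. If that number is 0 to 3 of 30 (an assumption), the overstatement is 0 to 3/30 = 10.0 points.

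**6. How often it can arise.** Section 5.1 allows at most three lesions, in one lobe. The target cap in the treated lobe is five in 9.1 and three in 9.1.1, so nearly every measurable liver lesion will be a target. The remaining non-target disease would be lesions under 10 mm, nodes of 10 to under 15 mm, ascites, or extrahepatic disease not judged significant. BCLC stage C is eligible, so these are uncommon but not excluded.

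**7. Markers.** No tumor marker appears in the screening, mapping-day or 1-, 3- and 6-month lists of 8.1, or in the laboratory tables of 8.2. The schedule in 1.3 has only a general blood-sampling row. No marker is named anywhere in the response criteria.

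**8. Other endpoints.** Section 10.5.4 defines TDRT by CR or PR together, so a CR/PR exchange leaves it unchanged. It is not a progression event either, so TTP and PFS do not move. The primary LSF and TNR comparison in 10.3 does not use response.

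**The case against.** The strongest reply is that this is a copying slip which a competent reader would see through. The literal reading yields non-target PR and SD, which the table cannot accept, so the reader is driven back to the recorded terms. Absent, present and unequivocal progression map naturally onto CR, Non-CR/Non-PD and PD. Independent review is also already planned in Section 8 and under Response Review in 9.1.2.

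Much of that stands. It shows that the intended rule can be recovered and that the repair is small. It does not show that the plan states the rule. Independent reviewers need written criteria as much as the site does, and for target CR with a persisting non-target site the printed definition gives a definite, wrong answer.

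A reader might infer that non-target disease never affects response, or that progression outside the targets will be missed and will bias TTP and PFS. The documents do not support that. The 9.1.2 table turns any non-target PD into overall PD, its footnote accepts unequivocal non-target progression, and 9.1.1 lets the physician call it with later confirmation. The copied PD definition contradicts those routes but does not close them.

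On markers, the sentence speaks of complete clinical response, which may have been meant as something other than the imaging CR of 9.1.1. The plan does not say so, which is why it needs reconciling. It does not establish that two definitions of the CR endpoint were intended.

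**Conclusion.** The non-target block in 9.1.1 is wrong as written. It contradicts the qualitative follow-up in 9.1 and 9.1.1 and leaves the 9.1.2 table without the non-target categories it uses. The consequence that follows directly is a possible overstatement of the CR rate in 10.5.3, of about 3.3 points for each affected patient with 30 evaluable and more with fewer. The total cannot be estimated from the documents, and the entry limits suggest it is small. The primary analysis is unaffected.

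The marker condition is a lesser inconsistency: it is absent from the CR definitions and cannot be applied from scheduled data. This assumes that no marker is scheduled in a document outside the protocol, such as a laboratory manual.

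The point should be corrected before responses are read, but it does not threaten the trial's main conclusion.

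**What to change.** Replace the four non-target definitions in 9.1.1 with the three categories the 9.1.2 table uses, tied to what is already recorded:

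- **CR:** all non-target lesions absent; for lesions in the liver, no arterial enhancement. Enhancement alone would not suit nodes or ascites, so absence has to be the general term.
- **Non-CR/Non-PD:** one or more non-target lesions present, without unequivocal progression.
- **PD:** unequivocal progression of a non-target lesion, confirmed for the endpoint by the independent review already planned in Section 8 and 9.1.2.

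Reconcile the tumor-marker sentence in 9.1 with 9.1.1 and 9.1.2. Since no marker is scheduled, state that CR for the 10.5.3 analysis rests on imaging alone, and remove the normalization condition from that endpoint.

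The cost is wording only. Presence, absence and unequivocal progression are already to be noted, and no visit, scan or blood test is added. The one downside is that the CR rate may come out slightly lower than under the present text.

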9.1.2 Evaluation of Best Overall Response

The best overall response is the best response recorded from the start of the treatment until disease progression/recurrence (taking as reference for progressive disease the smallest measurements recorded since the treatment started). The patient's best

response assignment will depend on the achievement of both measurement and confirmation criteria.

For Patients with Measurable Disease (*i.e.*, Target Disease)

Target Lesions	Non-Target Lesions	New Lesions	Overall Response	Best Overall Response when Confirmation is Required*	
CR	CR	No	CR	≥4 wks. Confirmation**	
CR	Non-CR/Non-PD	No	PR	≥4 wks. Confirmation**	
CR	Not evaluated	No	PR		
PR	Non-CR/Non-PD/not evaluated	No	PR	Documented at least once ≥4 wks. from baseline**	
SD	Non-CR/Non-PD/not evaluated	No	SD		
PD	Any	Yes or No	PD	no prior SD, PR or CR	
Any	PD***	Yes or No	PD		
Any	Any	Yes	PD		

* See RECIST 1.1 manuscript for further details on what is evidence of a new lesion.
 
** Only for non-randomized trials with response as primary endpoint.
 
*** In exceptional circumstances, unequivocal progression in non-target lesions may be accepted as disease progression.
					

Note: Patients with a global deterioration of health status requiring discontinuation of treatment without objective evidence of disease progression at that time should be reported as “symptomatic deterioration.” Every effort should be made to document the objective progression even after discontinuation of treatment.
					

For Patients with Non-Measurable Disease (*i.e.*, Non-Target Disease)

Non-Target Lesions	New Lesions	Overall Response
CR	No	CR
Non-CR/non-PD	No	Non-CR/non-PD*
Not all evaluated	No	not evaluated
Unequivocal PD	Yes or No	PD
Any	Yes	PD

* ‘Non-CR/non-PD’ is preferred over ‘stable disease’ for non-target disease since SD is increasingly used as an endpoint for assessment of efficacy in some trials so to assign this category when no lesions can be measured is not advised
		

Duration of Response

Duration of overall response: The duration of overall response is measured from the time measurement criteria are met for CR or PR (whichever is first recorded) until the first date that recurrent or progressive disease is objectively documented (taking as reference for progressive disease the smallest measurements recorded since the treatment started).

The duration of overall CR is measured from the time measurement criteria are first met for CR until the first date that progressive disease is objectively documented.

Duration of stable disease: Stable disease is measured from the start of the treatment until the criteria for progression are met, taking as reference the smallest measurements recorded since the treatment started, including the baseline measurements.

Progression-Free Survival

PFS is defined as the time from the date of first dose to the date of the first objectively documented progressive disease per m-RECIST or death, whichever is earlier. Patients who do not have the date of disease progression per m-RECIST or date of death will be censored on the date of the last evaluable tumor assessment. Patients who started a new antineoplastic regimen prior to disease progression per m-RECIST will be censored on the date of the last evaluable tumor assessment prior to receiving the new antineoplastic regimen. Patients whose disease progression or death appears after missing two consecutive tumor assessments will be censored on the date of the last evaluable tumor assessment. Patients who are lost to follow up will be censored on the date of their last evaluable tumor assessment. PFS will be estimated using the Kaplan-Meier method. The median and its 95% CI, along with the 25% and 75% quartiles will be summarized for all treated patients. OS will be defined as the date of first dose to the date of death. Patients who do not have a date of death will be censored on the last date for which the patient was known to be alive. OS will be analyzed similarly to PFS.

Response Review

All responses will be reviewed by an expert(s) independent of the study simultaneously as the results become available.

10. STATISTICAL CONSIDERATIONS

10.1 Study Design/Endpoints

Primary Objective Endpoints:

A) Accuracy/Efficacy: The accuracy/efficacy of MAA as a predictor of therapeutic Y90 distribution will be compared to that of low-dose Y90.

H₀: Y90 will have the same LSF as MAA.

H_A: Y90 will have significantly less LSF than MAA.

H₀: Y90 will have the same TNR as MAA.

H_A: Y90 will have significantly higher TNR than MAA.

B) Safety: adverse events related to Y90 radioembolization and angiography will be document by physical examination, clinical laboratory test and cross-sectional imaging.

No statistical consideration applied to the safety portion of the primary end point as it is a single arm study in which every patients undergo both mapping procedures with MAA and low-dose Y90. Detailed safety analysis plan is outlined below in section 10.5.

10.2 Sample Size/Accrual Rate

Based on previously published data by our group, we assume mean (SD) LSF of 11.66% (10.2) for HCC using MAA[43]. Assuming LSF in low-dose Y90 is 50% lower than what is predicted by MAA and within subject correlation of 0.5 in a paired t-test, **n=30** achieves 80% power with $\alpha=0.05$. This assumption is based on several previously published studies including the work presented by our own that demonstrate that MAA overestimates true Y90 LSF by as high as 100% [25, 35-37]. Assuming mean (SD) TNR of 5.4 (2.1) using MAA is 30% lower than low-dose Y90, the power achieved with n=30 is greater than 99% [8, 25].

Emory University Hospital is one of the busiest liver transplant and cancer centers in United States. Annually, 150 HCC patients who may be transplant/surgical or palliative therapy candidates are referred to interventional radiology (IR) at Emory for liver directed therapies. Assuming a conservative accrual rate of 30%, we predict an enrollment of **n=30** patients in 6-8

months. In the event that a patient drops out either after being consented or after having a part of the study completed, a new patient will be recruited.

